1. LIST OF ACRONYMS

BUA	Biological Use Authorization
CDC	Center for Disease Control
CO	Corneal Opacity
DBS	Dried Blood Spot
DSMC	Data and Safety Monitoring Committee
DCC	Data Coordinating Center
DNA	Deoxyribonucleic Acid
GPS	Global Positioning System
IRB	Institutional Review Board
MOH	Ministry of Health
MOP	Manual of Procedures
NEI	National Eye Institute
NIH	National Institutes of Health
NRERC	National Research Ethics Review Committee
PCR	Polymerase Chain Reaction
PNSO	Programme National de Santé Oculaire
SAP	Statistical Analysis Plan
TF	Trachomatous Inflammation – Follicular
TI	Trachomatous Inflammation – Intense
TS	Trachomatous Scarring
TT	Trachomatous Trichiasis
TCC	Trial Coordinating Center
USAID	United States Agency for International Development
UCSF	University of California San Francisco
WHO	World Health Organization

2. INTRODUCTION

2.1 EXECUTIVE SUMMARY

We propose a randomized controlled trial of discontinuation versus continuation of annual mass azithromycin distribution in hypoendemic communities of Maradi, Niger. We will randomize communities with up to 20 % TF prevalence following at least 5 years of mass azithromycin distribution to discontinuation or continuation of 3 additional years of annual mass azithromycin distribution.

2.2 STUDY OUTCOMES

2.2.1 PRIMARY OUTCOME

The primary outcome will be ocular chlamydia as assessed by PCR, measured in a population-based sample of 0-9-year-old children at 36 months.

2.2.2 SECONDARY OUTCOMES

Secondary outcomes will include infectious load of chlamydia among 0-9 year-old children infected with ocular chlamydia, conjunctival inflammation as assessed from conjunctival photography, and seropositivity to chlamydia based on antibody response to Pgp3 and CT694 antigens. Infectious load is of interest as children with higher bacterial loads are thought to be more likely to transmit infection. By measuring infectious load, we will be able to estimate community bacterial load in addition to any effect on ocular chlamydia prevalence. Even if prevalence is the same in treated and untreated communities, it is possible that treatment will lower infectious load in individuals with ocular chlamydia.

2.3 METHODS

2.3.1 RESEARCH DESIGN

We propose a community randomized controlled trial to evaluate if mass azithromycin distribution can be discontinued in low prevalence districts. We propose to randomize *grappes* (communities with 200 to 2,000 residents) in Niger to continuation of annual mass azithromycin distribution to the entire community or discontinuation of azithromycin treatment.

2.3.2 STUDY AREA

This study will be conducted in two districts in Maradi Region, Niger. The districts of Guidan Roumdji and Mayahi have approximately 1 million inhabitants. Per the most recent trachoma impact surveys, conducted in July 2018, these districts have TF prevalence up to 20%. Annual mass azithromycin distribution started in 2008 in Guidan Roumdji and Mayahi.

2.3.3 SAMPLE SIZE

40 communities per arm (80 total) will be included in the study. Please see Statistical Analysis Plan (SAP) for same size calculation details.

2.3.4 STUDY PERIOD

The study will take place over a three-year period.

3. ORGANIZATION AND POLICIES

3.1 STUDY ORGANIZATION

3.1.1 STUDY PARTNERS

The Proctor Foundation and PNSO are natural partners to conduct the proposed research. They have worked together on a Gates Foundation-funded cluster-randomized trial of mass azithromycin distribution in Niger. The research partners complement each other, with the Proctor Foundation providing expertise in study design and analysis, and PNSO implementing the fieldwork in a thorough yet efficient manner.

3.1.2 EXECUTIVE COMMITTEE

The Executive Committee will consist of Drs. [name] and [name] from the Proctor Foundation and [name] from PNSO. This committee will act as the administrative and executive arm of the clinical trial and will

meet in person twice a year to provide overall oversight for the study and make decisions on day-to-day operation issues, including:

- Supervise study progress and data collection progress
- Discuss any quality control issues that have arisen in the Trial Coordinating Center (TCC) and Data Coordinating Center (DCC)
- Evaluate and adopt changes in study procedures as necessary
- Communicate with and implement recommendations from the Data and Safety Monitoring Committee (DSMC)
- Make executive decisions on the allocation of resources
- Establish policies on publications and authorship
- Approve and oversee ancillary studies

3.1.3 TRIAL COORDINATING CENTER (TCC)

The TCC will be located at the Proctor Foundation. [name] will lead the center, which will also include [name] (co-PI), [name] (biostatistician), [name] (co-investigator), [name] (statistical analyst), and [name] (Proctor program manager). The role of the TCC will be to oversee and coordinate the overall implementation of the trial. Specifically, this means maintaining an up-to-date manual of operations and procedures, obtaining ethical approvals from all involved parties (UCSF, Niger MOH), conducting training and certification of all study personnel, ensuring proper masking of outcome assessment, and monitoring adherence and adoption of the study intervention. The TCC will organize site visits at least once per year before each monitoring visit to conduct training sessions with outcome assessors and monitor the quality of data collection. The principal investigators and Proctor program manager will be present at all site visits. The Proctor program manager, with assistance from the PNSO study coordinator, will organize the training sessions. The TCC will meet officially as a group at least four times per year. All members of the TCC are currently working on studies of trachoma in Ethiopia and Niger. The group has close working relationships with the PNSO staff in Niger and expertise with cluster-randomized trials in resource-poor settings.

3.1.4 NIGER COORDINATING CENTER

The Niger Coordinating Center will be located at the PNSO headquarters in Niamey, Niger. The center will be led by the study site principal investigator, [name], and also include [name], the PNSO study coordinator. [name] will oversee the study activities that take place in Niger and will manage the day-to-day activities of the PNSO study coordinator. He will also assist with obtaining ethical approval from appropriate federal, regional, and zonal agencies. The PNSO study coordinator will work with the local health officials to find health extension workers for the census activities and nurses to work as data collectors. He will supervise all data collection activities and will be responsible for proper storage and transport of specimens.

[figure not shown]
3.1.5 DATA COORDINATING CENTER (DCC)

The DCC will be located at the Proctor Foundation and led by [name]. The Proctor Foundation has served as a DCC for several other trials, including the cluster-randomized trials of trachoma in Ethiopia (TANA and continuation study, NEI U10 EY016214) and Niger (MORDOR; Gates OPP 1032340), and individually randomized trials of corneal ulcer treatment and prevention in India (SCUT, NEI U10 EY015114; MUTT, NEI U10 EY018573) and Nepal (VIEW, NEI U10 EY022880). [name], along with [name] (statistical analyst) will be responsible for data management, data quality control, event adjudication, and training and certification of enumeration personnel. The DCC will be responsible for drafting the trial's statistical analysis plan, analyzing data according to the plan, and providing data requested for publications. The DCC will be responsible for coordinating and supervising the activities of the Data and Safety Monitoring

Board, including preparing interim and final data reports. The DCC will also be responsible for coordinating the use of the electronic data capture system, including maintenance of the software application and data backup monitoring visits. The DCC will meet monthly. The DCC will be in close contact with the Proctor study coordinator, who will help address any issues with her counterpart in Niger.

3.1.6 DATA SAFETY AND MONITORING COMMITTEE (DSMC)

The DSMC will be formed according to NIH guidelines and is comprised of independent experts in bioethics, biostatistics, epidemiology, ophthalmology, and global health. The DSMC will meet at least once per year. Ad hoc meetings may be convened as necessary. The DSMC will approve the trial protocol at the first meeting, or recommend modifications to the protocol as necessary. At annual meetings, the DSMC will review data on efficacy outcomes. They will also monitor for unanticipated events.

3.2 COLLABORATING INSTITUTIONS

3.2.1 FRANCIS I. PROCTOR FOUNDATION

The Proctor Foundation is an organized research unit at the University of California, San Francisco. The Foundation has a more than 60-year history of research in ocular infectious and inflammatory diseases and runs one of the leading corneal fellowship training programs in the United States. Proctor Foundation faculty have been involved in the prevention of blindness research in developing countries since the foundation's inception. The impetus for establishing the foundation in 1947 was to eradicate trachoma in the American Southwest and other parts of the world. From this initial inception, the Foundation has expanded research efforts to include the other major causes of blindness worldwide, with a continuing emphasis on infectious and inflammatory eye diseases. The Proctor Foundation will be the main coordinating center for the study. [name] and [name], the Principal Investigators of this study at the Proctor Foundation, will be assisted by several co-investigators, one study coordinator, a microbiologist, a data management specialist, laboratory PCR processing staff, and a biostatistician.

3.2.2. PROGRAMME NATIONAL DE SANTE OCULAIRE (PNSO)

The Programme National de Sante Oculaire is an institution housed in the Ministry of Health in Niamey, Niger. PNSO is responsible for development and evaluation of the National Eye Health Program of Niger, with the goal of reducing visual impairment and the prevalence of blindness in Niger. PNSO is also involved in research related to preventable blindness in Niger. The coordination team of PNSO consists of 3 ophthalmologists, 1 manager, 1 coordinator, 1 epidemiologist, and 2 drivers on the full-time staff. PNSO has administrative and financial offices, a data management unit, and has close ties to district hospitals in Maradi and other regions throughout Niger. The capacity and experience of the personnel at PNSO and their close connections with communities involved in the project will ensure the success of proposed work.

3.3 DUTIES AND RESPONSIBILITIES OF STAFF

3.3.1 PRINCIPAL INVESTIGATORS (PROCTOR FOUNDATION)

- Develop study design, specific aims, and outcome measures, with help of biostatistician, study coordinators, and partners
- Obtain grant funding with help of partners, develop grant budget
- Ensure that staff follow through on protocol and properly execute all areas of research
- Ensure that all ethical approval is maintained
- Write or add major contributions to all study-related publications
- Ensure proper masking procedure for staff involved in the study
- Supervise training certification for all trachoma examiners

3.3.2 STUDY COORDINATOR (PROCTOR FOUNDATION)

- Ensure the execution of the study per protocol
- Coordinate with the collaborating center, PNSO, particularly with the PNSO Study Coordinator in execution of the study
- Manage correspondence between all collaborating organizations and parties
- Maintain all ethical clearances for the study, including IRB renewals, NRERC, and BUA and DSMC-related approvals
- In collaboration with PNSO Study Coordinator, prepare all forms and documents necessary for fieldwork (randomized registration forms, exam sheets, fieldwork documents directing team, etc)
- Train census workers in the use of electronic data capture system (with help of PNSO Study Coordinator)
- Train both Proctor and Nigerien health worker teams for each collection visit; direct team (with help of PNSO Study Coordinator) while in Niger
- Arrange logistics and itineraries for traveling team members in Niger
- Purchase, maintain, and organize transport of all necessary study supplies to/within Niger
- Maintain communication and partnership with Principal Investigators regarding all study activities and plans

3.3.3 STUDY COORDINATOR (PNSO)

- Prior to the start of the study, secure support from the Ministry of Health
- At baseline, obtain permission from the district health leaders; meet with and obtain written consent from all community leaders

- Supervise and train collection team (with emphasis on any new members) throughout each collection, especially after departure of Proctor team
- Train and supervise all census taking teams, including training in the electronic data capture system
- Charge all tablet computers and battery packs each night of the census
- Train and supervise all Zithromax distribution teams
- Maintain all fieldwork documents and records
- Complete all collection and intervention reports
- Work with Data Coordinator to maintain treatment and census database
- Oversee transport of study samples
- Assist Proctor Coordinators in coordinating logistics in Niger
- Train and supervise enumeration staff at PNSO in Niamey
- Analyze and provide data when requested by co-investigators or staff from Proctor
- Appropriately back up all data

3.3.4 CO-INVESTIGATORS (UNITED STATES AND NIGER)

- Assume responsibility for the study in the absence of the Principal Investigators
- Supervise ophthalmic assistants, ophthalmic nurses, local health agents, and other Proctor field team members in the field to ensure conformity to study procedures
- Communicate with Study Coordinator and Principal Investigators to ensure the execution of the study per the protocol

3.3.5 STATISTICAL ANALYST (PROCTOR FOUNDATION)

- Create and maintain the database for all collection and results-related data for the study:
 - Monitor correct receipt of data after each collection visit
 - Develop consistency checks in the data management – verify any inconsistencies or question regarding data through communication with Study Coordinator
 - Analyze and provide data regarding collection and results for study staff when needed, such as for publications or DSMC meeting
 - Back up all data appropriately
 - Follow up on any missing data or lab results

3.3.6 BIostatistician (PROCTOR FOUNDATION)

- With the Principal Investigators, create the Statistical Analysis Plan (SAP)
- Receive all study data and review for quality control purposes
- Ensure appropriate masking
- Prepare data analysis plan for DSMC meetings; oversee analysis and prepare all presented data for DSMC meetings, DSMC reports, and all study publications

3.3.7 TREATMENT AND CENSUS TEAM

- PNSO will hire and train “health extension workers” to perform the census

- During census phase, travel to the enrolled clusters and obtain patient information as required for all census forms. The census will be performed with an electronic data capture system, with the following data inputs for each household member:
 - Name
 - Gender
 - Age
 - GPS coordinates of each household
 - GPS coordinates for each safe water source in the study area
 - GPS coordinates for each school in the study area
- During the treatment phase:
 - Complete training by PNSO Study Coordinator and officials from District Health Department regarding proper treatment protocols and procedures
 - Travel to enrolled clusters and administer study medication to the study subject per protocol
 - Directly observe consumption of study drug
 - Record antibiotic coverage against previous census
 - Return to households until they have distributed antibiotics to at least 80% of individuals
 - Counsel and motivate participants for follow-up and monitoring visits
 - Inform patients of available health care facilities and procedures in local health centers and hospitals
 - Collect information on the nature of any Adverse Events experienced by study participants, and report this information immediately to PNSO investigators

3.3.8 COLLECTION TEAM

- At each collection phase, complete on-going training and certification in clinical examination and collection procedures
- Prepare all study-related materials before travel to study sites
- In each cluster, mobilize and identify all randomly selected participants
- Explain study purpose and procedure and obtain verbal consent for enrollment from each participant or participant guardian
- Under supervision of PNSO Study Coordinator and/or trained Proctor staff, perform clinical exam for each patient and collect all participant study samples according to protocol; store and record all samples correctly for transport, organization, and processing
- Counsel and motivate participants for follow-up and monitoring visits
- Inform patients of available health care facilities and procedures in local health centers and hospitals
- Collect information on the nature of any Adverse Events experienced by study participants, and immediately report to PNSO investigators

3.4 POLICY MATTERS

Any changes to the protocol made during the course of the study will be incorporated into the revised protocol and the Manual of Operations and Procedures (MOP) and recorded in a change log. Any new forms will be incorporated as an addendum. The protocol changes should be submitted and approved by the IRB of both the collaborating centers and by the DSMC.

3.5 PRESENTATIONS AND PUBLICATIONS

All presentations and publications should include acknowledgement of funding sources and give credit to the collaborating organizations and/or individuals involved.

3.5.1 AUTHORSHIP POLICY

Acknowledgements will include grant source(s) and/or NIH grant(s) as well as the DSMC.

4. PARTICIPANT FLOW

4.1 ELIGIBILITY REQUIREMENTS

4.1.1 INTERVENTION ELIGIBILITY

All individuals in all clusters will be eligible for randomization to continuation or discontinuation of mass distribution of azithromycin.

4.1.2 MONITORING ELIGIBILITY

Monitoring will be based on population-based samples. The following groups will be monitored at each study visit: 1) a random sample of 50 children aged 0-9 years will receive conjunctival photography and swabbing; 2) a random sample of 40 children aged 1-9 years will receive dried blood spot collection. Eligibility for these groups will be based on the previous census.

4.2 RANDOMIZATION

4.2.1 CLUSTERS

The randomization unit for this trial will be the grappe.

4.2.2 CONTAMINATION

Cluster-randomized trials are subject to contamination between clusters, which could weaken observed effects of the intervention if intervention activities occur in non-intervention clusters. Contamination will be minimized in this study because study activities (e.g., census and treatment) will not be available in areas not randomized to the intervention. We also reduce the chances of contamination by choosing relatively large geographic area, the grappe, as the randomization unit, and by choosing a sentinel development team for monitoring in each grappe from within this unit. This increases the distance between clusters and creates a buffer zone that reduces admixture between intervention and control groups.

4.2.3 TREATMENT ARM RANDOMIZATION

Study communities will be randomized into one of the 2 study arms after the baseline monitoring visit. Randomization will occur after the baseline monitoring visit to reduce the potential for differential outcome assessment at the baseline visit. The randomization sequence will be generated by the trial biostatistician in San Francisco using a random number generator, without stratification or blocking.

4.3 MASKING

Given the nature of the intervention, participants and investigators will not be masked as to study arm. Census workers who conduct the census will be masked to treatment arm of the study community, as will outcome assessors conducting clinical examinations and collecting swabs. Laboratory personnel processing conjunctival swabs for ocular chlamydia and dried blood spots for serology will be masked to treatment group and to control versus study samples. Photographs will be graded by a masked grader. All samples and photographs will be processed in a random order. Masking will not only minimize bias introduced through knowledge of treatment assignment but will ensure that the census and outcome assessment is identical in all study communities.

5. CENSUS

We will perform a house-to-house census of the selected study communities at baseline prior to randomization. The census will be updated at 36 months. PNSO will organize and train existing health extension workers to perform the census. Health extension workers in Niger are experienced in census-taking, and PNSO has experience in conducting large censuses in Niger, as they conduct a census every year. We will use an electronic data capture system for the census, as is currently being used in the Gates Foundation funded MORDOR Burkina Faso study. This system utilizes tablet computers to record all census data. Census workers will record the name, gender, and age of each household member. Each tablet has GPS capability, and coordinates will be recorded for each household in the study area with the tablet.

5.1 EQUIPMENT

Each census worker will be given the following equipment:

1. Tablet computer: LG Stylo 5 (1)
2. Battery pack: New Trent iCarrier 12000 mAh Dual Ports 2A/1A charger (1)
3. Charging cord (from charger to electrical socket) (1)
4. Connecting cord (from computer to charger) (1)
5. Speck protective case (1)
6. Sealable canvas bag to hold all equipment (1)

5.2 MOBILE APPLICATION

A custom-made software application, which runs on the Android platform, will be used for data collection in the study. The software application will be created through CommCare. Census workers will enter all data directly into the application.

5.3 TRAINING

The study coordinators from the Proctor Foundation and PNSO will run a 2-day training workshop for all census takers to train them in the following topics:

1. General use of tablet computers
2. Entering data into the mobile application
3. Acquiring GPS coordinates with the device
4. Re-charging the device

5.4 CHARGING DEVICES

The PNSO coordinator will be responsible for charging all devices each night. This will be done at the coordinator's hotel, which must be equipped with a backup generator. The study coordinator will be charging 20 devices and 20 chargers per night, so will bring sufficient power strips for this task.

6. STUDY INTERVENTIONS

The cluster-randomized trial consists of two arms: 1) annual mass azithromycin distribution to all residents per WHO guidelines (*Continue Treatment*); 2) discontinuation of mass azithromycin distribution (*Stop Treatment*).

6.1 INTERVENTION

6.1.1 MASS AZITHROMYCIN DISTRIBUTION

In all study communities randomized to the annual treatment arm, all individuals aged 1 month and older will receive a single mass distribution of azithromycin several weeks after the baseline monitoring visit, and then annually for 3 years. Oral azithromycin, 20 mg/kg for children and 1 g for adults, will be offered to all households identified on the preceding census in the communities randomized to continuing treatment. Study drug will be distributed by health extension workers and organized by PNSO. Individuals with a known macrolide allergy will be offered a two-week course of daily ophthalmic tetracycline ointment (two tubes).

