10. TREATMENT

10.1 MASS AZITHROMYCIN DISTRIBUTION

All individuals in communities randomized to azithromycin continuation will receive one annual mass distribution of azithromycin after baseline census and monitoring. During the mass treatment, all individuals aged 1 month and older will be offered a single dose of directly observed oral azithromycin (1g for adults and 20mg/kg for children). Children under 1 month, pregnant women, and those with known macrolide allergies will be offered two tubes of tetracycline ointment to be used twice daily for 6 weeks. Antibiotic coverage will be assessed relative to the preceding census population. Workers will return to households until they distribute antibiotics to at least 80% of individuals. In previous studies, we have routinely achieved >85% antibiotic coverage.

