10.2 ELIGIBILITY

During the mass treatment, all individuals in communities randomized to azithromycin continuation aged 1 month and up will be offered a single dose of oral azithromycin, 20mg/kg for children using height-based dosing and 1g for adults. Those under 1 month of age, pregnant, or macrolide-allergic would be offered 2 tubes of topical tetracycline ointment, to be used twice daily.

All age groups and sexes are eligible to receive study drug as per each study arm outlined above, except those contraindicated by the Ministry of Health, which include:

- Those self-reported as pregnant
- Those known to be allergic to azithromycin or macrolides such as erythromycin

These three exceptions will be treated with topical tetracycline eye ointment. Women uncertain of their pregnancy status may be offered an immediate-result pregnancy test if deemed appropriate by ethics committees.

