11.2. DOSAGE INFORMATION

Azithromycin will be administered as a single dose, in tablet form for adults and in oral suspension form for children. Dosing will be as per the WHO recommendations for treatment of active trachoma:

- 1) Single dose of one gram of azithromycin for adults
- 2) Single dose of 20mg/kg in children (up to the maximum adult dose of 1g)
- 3) Height-based dosing of children will be acceptable, as per PNSO’s program—note that this is supported by the WHO PBD group.

Individuals who are either under the age of 1 month, pregnant, or allergic to macrolides/azalides will be treated with 1% tetracycline eye ointment to be applied twice daily to both eyes for a 6 week period. If the appropriate ethical committee in Niger suggests pregnancy tests for self-reported pregnant women, or if the women are unsure of their pregnancy status, then they may be offered an on-site pregnancy test.

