12.4 INCLUSION OF PREGNANT WOMEN AND CHILDREN

All participants, regardless of gender, will be accepted. We will obtain informed consent from all study participants prior to entering the study. Pregnant women and children under 1 month will be excluded from receiving study drug, and will be offered topical tetracycline eye ointment in its place.

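### Protocol 6.1.1 gives macrolide-allergic people a different tetracycline course from 10.1 and 11.2, and omits the pregnancy and under-1-month provisions stated elsewhere

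*Protocol*

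**What the plan says.** Six places state who is not given azithromycin, what they are offered instead, or both.

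- **Protocol 6.1.1** describes the continuation arm: "all individuals aged 1 month and older will receive a single mass distribution of azithromycin several weeks after the baseline monitoring visit". Its only alternative pathway is for allergy: "Individuals with a known macrolide allergy will be offered a two-week course of daily ophthalmic tetracycline ointment (two tubes". It does not mention pregnancy, and offers nothing to infants under 1 month.
- **Protocol 10.1** names three groups: "Children under 1 month, pregnant women, and those with known macrolide allergies will be offered two tubes of tetracycline ointment". The course is "will be offered two tubes of tetracycline ointment to be used twice daily for 6 weeks" in full.
- **Protocol 10.2** names the same three groups and gives a frequency but no duration: "Those under 1 month of age, pregnant, or macrolide-allergic would be offered 2 tubes of topical tetracycline ointment, to be used twice daily". Its bulleted list of Ministry of Health contraindications then has two entries, pregnancy and allergy, followed by "These three exceptions will be treated with topical tetracycline eye ointment".
- **Protocol 11.2** covers the same three groups, with 1% ointment "to be applied twice daily to both eyes for a 6 week period".
- **Protocol 12.4** states: "Pregnant women and children under 1 month will be excluded from receiving study drug". It offers them tetracycline ointment and gives no regimen.
- **SAP 5.2** repeats the sentence from Protocol 10.2, again without a duration.

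**The concern.** The treatment rules should read the same wherever a distributor or trainer might look them up, and here they do not. A person with a macrolide allergy is given one ointment course in the section on study interventions and another in the sections on treatment and medication. A reader who stops at 6.1.1 finds no instruction to divert pregnant women from azithromycin.

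What is at stake is how people are treated, rather than the trial's estimate. SAP 4.2 refers to the document as the study protocol / manual of procedures, and its last section is the MOP change log. Protocol 3.3.7 has the treatment team give the drug according to protocol, and Protocol 6.2 has distributors trained before each round. Protocol 12.3 limits treatment risk by restricting the drug to people in the approved age and inclusion category. That safeguard needs one agreed statement of the category.

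**Working it through.** The plan has no figure to reproduce here. The check is a comparison of the passages, followed by a small count.

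**Step 1. Passages side by side**

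| Place | Groups offered ointment | Frequency | Duration | Supply |
|---|---|---|---|---|
| Protocol 6.1.1 | allergy | daily | 2 weeks | two tubes |
| Protocol 10.1 | under 1 month, pregnant, allergy | twice daily | 6 weeks | two tubes |
| Protocol 10.2 | under 1 month, pregnant, allergy | twice daily | not stated | two tubes |
| Protocol 11.2 | under 1 month, pregnant, allergy | twice daily, both eyes | 6 weeks | not stated |
| Protocol 12.4 | under 1 month, pregnant | not stated | not stated | not stated |
| SAP 5.2 | under 1 month, pregnant, allergy | twice daily | not stated | two tubes |

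**Step 2. Ointment course.** The macrolide-allergic group is the only one given a regimen both in 6.1.1 and in 10.1 and 11.2, so the direct conflict is confined to it.

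- Duration: 6 weeks / 2 weeks = 3. This needs no assumption.
- Applications, *assuming* daily in 6.1.1 means once a day: 1 × 14 days = 14, against 2 × 42 days = 84. The ratio is 84 / 14 = 6.
- If daily means only every day, 6.1.1 leaves the frequency open. The six-fold figure then lapses and the three-fold difference in duration remains.

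The supply does not settle the matter, because 6.1.1 and 10.1 state the same two tubes for courses of different length.

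**Step 3. Who is diverted from azithromycin.** Pregnant women are diverted in four protocol sections (10.1, 10.2, 11.2, 12.4) and in SAP 5.2, five places in all. Section 6.1.1 is silent. Infants under 1 month fall outside azithromycin in 6.1.1 as well, since the age threshold there is also 1 month. What 6.1.1 lacks for them is the tetracycline offer found in the same five places.

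**Step 4. Can something other than the plan explain it?** The passages are current text with no redaction in them, and the MOP change log has no entries.

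**Step 5. Reach into the analysis.** Protocol 10.1 and 11.7 compute coverage against the census population, a denominator that does not depend on these rules. SAP 4.2 uses eligible children. Pregnancy should not move that figure in the 0-9-year-olds the trial studies, and the azithromycin age threshold is the same in 6.1.1, 10.1, 10.2, 11.2 and SAP 5.2. Nothing in the sample size, margin or primary model uses the ointment regimen.

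**The case against.** The strongest reply is that 6.1.1 is a short description of the arm and that the documents as a whole give a consistent pregnancy rule. The section titled Eligibility, the dosage section, two other protocol sections and SAP 5.2 all divert pregnant women. SAP 4.2 points to Protocol section 11 for medication details, not to 6.1.1. Protocol 10.1 and 10.2 use similarly general wording about everyone aged 1 month and older, then state the exception. Protocol 3.3.7 also has teams trained by the national coordinator and district health officials, and Protocol 10.2 ties the pregnancy and allergy exclusions to the Ministry of Health.

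Much of this stands. For pregnant women the defect is an omission in 6.1.1, not an instruction to treat them. A reader might infer that distributors would give azithromycin to pregnant women. The documents do not support that, because nothing in them says that anyone is trained from 6.1.1 alone. A reader might also infer that coverage figures would be distorted, but the stated denominators do not bear that out. The mismatch in 10.2 between two bullets and three exceptions is editorial, since the paragraph above the bullets names all three groups.

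The reply does not reach the ointment course. For macrolide-allergic people, 6.1.1 gives a positive instruction that conflicts with 10.1 and 11.2, and no reading of the whole document removes the conflict.

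**Conclusion.** The point holds in two parts. First, the ointment course for macrolide-allergic people is contradictory: 2 weeks in 6.1.1 against 6 weeks in 10.1 and 11.2. That is three-fold in duration, and six-fold in applications only on the assumption that daily means once a day. Second, 6.1.1 is incomplete on pregnancy and on infants under 1 month.

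That field teams could treat the same people differently is a reasonable inference from the document's role as the manual of procedures; the documents do not report that it has happened. The point bears on the safety and consistency of treatment in the continuation arm, and no statistical consequence is claimed. It should still be corrected, because the stated rules cannot all be followed and the remedy is wording alone.

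**What to change.** Before distributors are trained, the sponsor and the ministry should reconcile Protocol 6.1.1, 10.1, 10.2, 11.2 and 12.4 and SAP 5.2. One list of groups not given azithromycin and one ointment regimen, with frequency, duration and supply, should then appear identically wherever they are stated, or be stated once and cross-referenced. The bulleted list in 10.2 should match the number of exceptions it announces. The choice of regimen and exclusion rule belongs to the sponsor and the ministry.

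The cost is protocol and SAP wording, with the approvals from both ethics boards and the DSMC that Protocol 3.4 asks for, and an entry in the change log. No design element, sample size or analysis changes.
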